7.1.2.6 Pain assessment

Pain experience will be assessed using:

- The Brief Pain Inventory (BPI): a widely used questionnaire for the assessment of pain intensity, location, and interference with activities of daily living in clinical and research settings [37].

7.1.2.7 Cardiorespiratory assessment

Basic cardiorespiratory function will be evaluated using:

- The mMRC Dyspnoea Scale [38]
- A standard 12-lead ECG performed after 10 minutes resting in the supine position
- A six-minute walk test: a sub-maximal exercise test used to assess aerobic capacity and endurance [39].

7.1.2.8 Laboratory assessments

Blood sampling will be performed to collect samples for the following laboratory assessments:

- Full blood count: red cell count, haemoglobin, haematocrit, mean cellular volume (MCV), mean corpuscular haemoglobin (MCH), mean corpuscular haemoglobin concentration (MCHC), red cell distribution width (RDW), white cell count and differential (neutrophil count, lymphocyte count, monocyte count, eosinophil count, and basophil count), and platelet count
- Serum chemistry: serum sodium, potassium, chloride, bicarbonate, calcium (corrected), magnesium, phosphate, urate

- Liver function: total protein, albumin, total bilirubin, direct bilirubin, alkaline phosphatase (ALP), gamma-glutamyl transferase (GGT), alanine aminotransferase (ALT), aspartate aminotransferase (AST), lactate dehydrogenase (LDH)
- Renal function: urea, creatinine, estimated creatinine clearance (Cockcroft-Gault method), cystatin C
- Glucose metabolism: serum glucose, HbA1C
- Inflammatory markers: a multiplex cytokine panel will be run using Luminex technology at the Wits School of Physiology. Markers investigated will include hs-CRP, IL-1 β , IL-6, IL-8, TNF- α , soluble TNFR1, and MCP-1, but additional inflammatory markers may be included based on emerging reports in scientific literature
- DNA extraction for genotyping and sequencing at the Sydney Brenner Institute for Molecular Bioscience (SBIMB)
- HIV testing for participants consenting to this (optional).

A urine sample will be collected for:

- urinalysis via urine dipstick
- determination of the urine albumin-to-creatinine ratio
- pregnancy test for woman of reproductive potential.

Additional blood (50 mL) and urine (100 mL) samples will be stored for possible future analysis.

Details regarding blood and urine sample collection, handling and processing, and the assays (where applicable) will be documented in the Laboratory Manual.

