2.3.1 Rationale for specific sub-study focus areas

- **Psychiatric, pain and sleep assessments:** All are major features of reported Long-COVID and are associated with impact on quality of life [4,5,7,8,11]. Sleep disturbances are associated with chronic inflammation and immune activation.
- **Respiratory assessment:** SARS-CoV-2 is a respiratory virus, and most of the severe morbidity and mortality seen with COVID-19 is due to lung involvement. Respiratory symptoms, parenchymal, and functional abnormalities have been well-described and are common in survivors [9,13].
- **Cardiac assessment:** Significant myocarditis, both acute and chronic, has been described with COVID-19 infection, and concern expressed about long term effects on function [12,17].
- **Renal assessment:** Kidney injury is common with acute SARS-CoV-2 infection, and subclinical inflammation and injury may persist for many months, with progressive decline in kidney function [10].
- **Glucose metabolism assessment:** Diabetes is a strong risk factor for severe COVID-19 disease, as well as for Long-COVID and B-cell dysfunction, often irreversible, in survivors [11,18].
- **Genetic assessment:** SARS-CoV-2, COVID-19, and vaccination immune responses have notable clinical heterogeneity and interindividual differences, whether susceptibility to the virus, severity of COVID-19, or vaccine response, and may be partly ascribed to host genetic factors. Early host

genetic investigations have been limited to acute COVID-19 in European-ancestry individuals, with almost no attention to genetic correlations with Long-COVID [19,20,21].

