3. OBJECTIVES AND ENDPOINTS

Primary	
Objectives	Endpoints
To characterise Long-COVID in four cohorts of patients with previous SARS-CoV-2 infection (asymptomatic, symptomatic, severely symptomatic requiring hospitalisation, and those who were vaccinated prior to widespread community exposure).	Incidence, severity, and duration of Long-COVID symptoms.
Secondary	
Objectives	Endpoints
To describe the following characteristics in four cohorts of patients with previous SARS-CoV-2 infection (asymptomatic, symptomatic, severely symptomatic requiring hospitalisation, and those who were vaccinated prior to widespread community exposure): 
• Inflammatory markers• Psychological profiles• Psychosocial exposures• Work performance in employed participants	
• High sensitivity C-reactive protein (hs-CRP)• Interleukin-1β (IL-1β)• Interleukin-6 (IL-6)• Interleukin-8 (IL-8)• Tumour necrosis factor alpha (TNFα)• Tumour necrosis factor alpha receptor-1 (TNFR1)• Monocyte chemoattractant protein-1 (MCP-1)• Headache Impact Test-6 (HIT-6)• Patient Health Questionnaire-9• Generalised Anxiety Disorder 7• PTSD Checklist for DSM-5 - Civilian Version• Mood Disorder Questionnaire• Montreal Cognitive Assessment• Daily Fatigue Impact Scale• COVID-19 related stress questionnaire• Multidimensional Scale of Perceived Social Support• Perceived Stress Scale• Adverse Childhood Experiences tool• Normal activities and work productivity questionnaire

• Sleep quality and disorders• Pain experience• Cardiorespiratory function• Standard laboratory parameters• Renal function• Host genetic factors that may be associated with Long-COVID	
• Pittsburgh Sleep Quality Index• Epworth Sleepiness Scale• Berlin Questionnaire for risk of sleep apnoea• International Restless Legs Syndrome Severity Scale• Sleep quality and mood visual analogue scale• Brief Pain Inventory• Modified Medical Research Council (mMRC) Dyspnoea Scale• Six-minute walk test (distance)• Electrocardiogram (ECG) parameters and morphology• Full blood count• Serum chemistry• Liver function tests• Glucose, glycosylated haemoglobin (HbA1C)• Creatinine clearance• Cystatin-C• Urine dipstick parameters• Urine albumin-to-creatinine ratio• Genotyping results• DNA sequencing results
Exploratory Objectives	

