5.2 Recruitment

Potential participants may volunteer in response to advertised clinical trial information, or will be contacted in compliance with POPIA regulations and invited to participate in the informed consent process (Section 11.2) and attend the baseline visit. Written informed consent will be obtained prior to any screening, and study-specific assessments and procedures. The following platforms will be used to identify potential participants:

- Cohort 1:
 - Volunteers who had previous asymptomatic SARS-CoV-2 infection confirmed by a documented positive PCR/antigen/antibody test during routine screening (e.g. for travel, elective surgery or as part of contact tracing)
 - Participants enrolled into prophylaxis studies who had a documented PCR/antigen/antibody-positive test during routine screening but no symptoms of infection
 - Participants enrolled in self-sampling and antigen evaluation protocols with documentation of a positive PCR/antigen test during routine screening but no symptoms of infection.
- Cohort 2:
 - Volunteers who had previous symptomatic COVID-19 confirmed by a documented positive PCR/antigen test, and who were managed as outpatients
 - Participants enrolled in large, early treatment, antiviral studies in symptomatic outpatients
 - Participants enrolled into prophylaxis studies who developed symptoms of infection confirmed to be COVID-19 through a documented positive SARS-CoV-2 PCR/antigen test at the time
 - Participants enrolled in self-sampling and antigen evaluation protocols who developed symptoms of infection confirmed to be COVID-19 through a documented positive SARS-CoV-2 PCR/antigen test.
- Cohort 3:
 - Age- and gender-matched patients treated at the Helen Joseph Hospital and Charlotte Maxeke Johannesburg Academic Hospital Infectious Diseases department who were infected at approximately the same time as participants recruited for Cohorts 1 and 2.

- Cohort 4:

- Participants enrolled in a non-placebo arm of a COVID-19 vaccine trial who received a vaccine that has subsequently been proven to be effective, and who were subsequently confirmed to be infected with SARS-CoV-2 (symptomatic or asymptomatic) through a documented positive PCR/antigen/antibody test.

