7.1.2.4 Physical examination and vital signs

Height and weight (as measured in light indoor clothing or underwear only, but without shoes) will be measured, and body mass index (BMI) derived.

A symptom-directed physical examination will be performed (including at least a general, cardiorespiratory, and skin examination and other systems as indicated through reported symptoms).

Vital signs (blood pressure, pulse rate, respiratory rate, body temperature, and oxygen saturation [SpO_2]) will be measured after 5 min resting.

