9.1 Sample Size Determination

No formal sample size was calculated for this exploratory study. On-study findings may suggest that larger sample sizes are required to further analyse endpoints in specific groups, and further planning for this may be performed.

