9.2.2 Primary and secondary endpoints

All primary and secondary endpoints will be summarised descriptively overall, per cohort, and per disease status (Long-COVID or no Long-COVID) as relevant, and for various risk factors as deemed appropriate in this exploratory study. Associations between outcomes, COVID-19 history, vaccination status prior to and since infection, and COVID-19 risk factors for severe disease will be explored. Co-factors such as time since initial SARS-CoV-2 infection, and possible confounders such as vaccination, exposure to potential disease-modifying repurposed drugs, and undisclosed vaccination or prior infections, will be accounted for as relevant.

Raw genetic genotyping results will be quality controlled by experienced SBIMB bio-informaticists. Association and fine-mapping will be used to investigate links between host genetics and Long-COVID variables generated by the broader study.

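### The only filtration estimate named, Cockcroft-Gault creatinine clearance, is proportional to body weight, so cohorts not matched on weight can differ, or look alike, on this endpoint through body size alone

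*Protocol*

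**What the plan says.** Protocol section 7.1.2.8 lists the renal blood tests as "Renal function: urea, creatinine, estimated creatinine clearance (Cockcroft-Gault method), cystatin C". Urine dipstick and albumin-to-creatinine ratio are collected as well.

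The endpoint table in section 3 gives four secondary endpoints for renal function: "Creatinine clearance", cystatin C, urine dipstick parameters and "Urine albumin-to-creatinine ratio". The background for the renal assessment, in section 2.3.1, is that "subclinical inflammation and injury may persist for many months, with progressive decline in kidney function".

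On body size, section 7.1.2.4 says that height and weight "will be measured, and body mass index (BMI) derived". The protocol does not say whether actual, ideal or adjusted weight enters Cockcroft-Gault. It does not mention indexing to body surface area, and it does not link cystatin C to any estimate of GFR.

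On the comparison, section 9.2.2 states: "All primary and secondary endpoints will be summarised descriptively overall, per cohort, and per disease status". Section 4.1 says the four cohorts will be compared. The matching described for Cohort 3 in section 5.2 is on age and gender: "Age- and gender-matched patients treated at the Helen Joseph Hospital". Section 7.2 adds age and gender matching, where possible, between sub-study participants with and without Long-COVID. Weight and BMI are matching factors in neither place, and section 9.2.2 does not name them among its co-factors and confounders.

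**The concern.** Cockcroft-Gault returns a clearance in mL/min in which weight is a direct multiplier. Two people of the same age and sex with the same serum creatinine receive different clearances in exact proportion to their weights. That matters little when one person is described. It matters when group means are set side by side and the groups may differ in body size.

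The renal rationale is about subclinical injury and gradual decline, so the differences of interest may be modest. A body-size artefact of similar size would be read as a kidney finding, or would cancel one. The protocol already collects, for every participant, what is needed for an estimate that does not contain weight, but it names no such estimate.

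**Working it through.** The protocol gives no renal values, weights, standard deviations or sample size calculation (section 9.1: "No formal sample size was calculated for this exploratory study"), so there is no figure to reproduce. The check uses the algebra of the named method with assumed inputs.

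**Formula.** Clearance (mL/min) = (140 − age) × weight in kg / (72 × creatinine in mg/dL), multiplied by 0.85 in women.

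**1. Effect of weight alone.** Assume a man aged 50 with creatinine 1.0 mg/dL, so that clearance = 90 × weight / 72.

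- 70 kg: 87.5 mL/min
- 85 kg: 106.3 mL/min
- 100 kg: 125.0 mL/min

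From 70 to 100 kg the ratio is 125.0/87.5 = 1.43, which is +43%. The ratio is simply 100/70, so it is the same at any age, sex and creatinine.

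**2. A creatinine difference hidden by weight.** At 100 kg and creatinine 1.4 mg/dL, clearance = 90 × 100 / (72 × 1.4) = 89.3 mL/min. This nearly equals the 87.5 of the 70 kg man with creatinine 1.0.

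**3. The same men indexed to 1.73 m2.** Body surface area (Du Bois) = 0.007184 × height^0.725 × weight^0.425, with an assumed height of 175 cm. This gives 1.848 m2 at 70 kg and 2.151 m2 at 100 kg.

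- 70 kg, creatinine 1.0: 87.5 × 1.73/1.848 = 81.9
- 100 kg, creatinine 1.0: 125.0 × 1.73/2.151 = 100.5
- 100 kg, creatinine 1.4: 89.3 × 1.73/2.151 = 71.8

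The weight effect falls to 100.5/81.9 = 1.23, or about +23%. The two men in step 2 now separate, at about 72 against 82. Indexing reduces the dependence on weight but does not remove it. For people of equal height the remaining factor is (100/70)^0.575 = 1.23, whatever that height is.

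**4. What this does to a cohort mean.** Assume men aged 50 with creatinine 90 µmol/L (90/88.4 = 1.018 mg/dL) in both cohorts. Each kg of difference in mean weight then adds 90/(72 × 1.018) = 1.23 mL/min. With 100 per cohort (synopsis, Sample Size) and an assumed SD of 25 to 35 mL/min, a two-sample comparison would be nominally significant as follows:

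| Difference in mean weight | Difference in clearance | Chance of nominal significance |
|---|---|---|
| 5 kg | 6.1 mL/min | 24% to 41% |
| 10 kg | 12.3 mL/min | 70% to 94% |
| 15 kg | 18.4 mL/min | 96% to 99.9% |

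Creatinine is identical in every row. The planned analysis is descriptive, so the percentages only show how visible the artefact would be.

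**5. Muscle loss.** Lower muscle mass lowers creatinine, but it also lowers weight. The estimate changes by the factor (1 − weight loss)/(1 − creatinine fall). For a 20% fall in creatinine:

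- no weight loss: 1/0.8 = 1.25, +25%
- 10% weight loss: 0.9/0.8 = 1.125, +12.5%
- 20% weight loss: 0.8/0.8 = 1.00, no change
- 30% weight loss: 0.7/0.8 = 0.875, −12.5%

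The direction depends on which falls more in proportion.

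**The case against.** The strongest reply is that creatinine clearance is one of four renal secondary endpoints in an exploratory, descriptive study. Cystatin C does not contain weight and will be summarised in the same tables, as will the albumin-to-creatinine ratio and dipstick. A deficit masked in creatinine clearance could still show there. This stands: it limits the problem to one endpoint and gives partial protection. It does not repair that endpoint, which is the only one expressed as filtration.

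A second reply is that the SAP, which is not at hand, may derive an eGFR. That is possible, and nothing in the protocol prevents it. But the choice of Cockcroft-Gault is written into the protocol itself, so this is not a detail simply left to the SAP.

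A third reply is that the remedy has its own bias. Inflammation can raise cystatin C, and section 2.1 suggests an immune-mediated inflammatory mechanism for Long-COVID. A combined estimate compared by Long-COVID status could be affected. This also stands, and is why the combined version should not be shown alone.

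A reader might also infer more than the documents support:

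- **That the hospitalised cohort is heavier and will look falsely normal.** No cohort weights are given and no renal cut-off is set. The direction of any imbalance is unknown.
- **That muscle-depleted participants are necessarily overestimated.** Step 5 shows the bias can go either way or vanish.
- **That renal function rests on Cockcroft-Gault alone.** The endpoint table shows otherwise.
- **That the method misses a weight-free equation by about 28 units.** For the 100 kg man with creatinine 1.4, the 2021 creatinine CKD-EPI equation gives 142 × (1.4/0.9)^−1.2 × 0.9938^50 = 61 mL/min/1.73 m2. Setting this against 89 mL/min mixes indexed and unindexed units. Put back on the mL/min scale at 175 cm, it is 61.2 × 2.151/1.73 = 76, a gap of about 13.

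**Conclusion.** The point holds as a limitation of one named secondary endpoint that is cheap to correct. It is neither a contradiction nor an arithmetical error in the protocol. Creatinine clearance by Cockcroft-Gault varies with weight at fixed creatinine, by 43% between 70 and 100 kg as the formula stands and by about 23% if indexed. It is to be summarised across groups not matched on weight, so a weight imbalance in either direction can create or mask a difference.

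The 43% follows from the formula alone. The 23% assumes equal height (175 cm used) and the Du Bois formula. The cohort figures rest on assumed age, creatinine and SD. Whether the cohorts actually differ in weight cannot be known from the protocol.

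**What to change.** In section 7.1.2.8 and in the endpoint tables (synopsis and section 3), add eGFR per 1.73 m2 by a race-free CKD-EPI equation, and make it the filtration measure for comparisons between cohorts and by Long-COVID status. Use the combined creatinine and cystatin C version, with creatinine-only and cystatin-C-only versions beside it, so that a cystatin C value raised by inflammation can be recognised.

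Keep Cockcroft-Gault as a supporting listing, and state which weight it uses and whether it is indexed.

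Creatinine, cystatin C, age and sex are already collected on everyone, so no extra sample or visit is needed. The cost is a few derived variables, a few more table rows and short wording changes. The downside is that three versions may disagree, and the report will have to explain this.

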7.1.3 Telephonic follow-up (up to 28 days after completion of baseline visit)

Participants will be contacted telephonically within 28 days of completion of their baseline visit to inform them of the results of their assessments. Abnormalities detected in assessments (suggesting undiagnosed medical or mental health issues) will be managed by on-study medical personnel with referral as appropriate.

7.2 Sub-Studies

Participants may be invited to take part in more than one sub-study, or none. Up to 30 participants from each cohort will be enrolled into each sub-study. Participants with and without Long-COVID will be age- and gender-matched where possible.

7.2.1 Screening and informed consent

Separate informed consent will be obtained for each sub-study for participants invited to take part in these.

7.2.2 Sub-study visit(s)

7.2.2.1 Respiratory evaluation

Participants who are selected and provide consent for participation in the respiratory sub-study, will attend a single visit where the following will be performed:

- mMRC Dyspnoea Scale

- High-resolution CT scan of the chest
- A full set of lung function studies, including full spirometry and DLCO.

Depending on findings at this visit, participants may continue to be followed up for a further 3- to 6-month period.

Further details can be found in the Respiratory Sub-Study Plan.

7.2.2.2 Cardiac evaluation

Participants who are selected and provide consent for participation in the cardiac sub-study, will attend up to three additional visits where the following will be performed:

- Clinical history and examination
- Serial blood pressure measurements
- Six minute walk test (distance)
- ECG
- Echocardiogram including speckle tracking
- Cardiac MRI
- Blood sampling for:
 - CK-MB
 - cTnT
 - pro-BNP.

Coronary angiography may be performed at the discretion of the treating cardiologist and dependent upon the clinical setting in patients with a clinical indication for diagnostic coronary angiography (e.g., acute coronary syndromes, unstable angina).

Further details can be found in the Cardiac Sub-Study Plan.

7.2.2.3 Psychiatric and neuroendocrine evaluation

Participants who are selected and provide consent for participation in the psychiatric and neuroendocrine sub-study, will have the following additional assessments performed:

- Repeated administration of questionnaires related to the psychological impact of COVID-19
- 4-day home collection of cortisol samples, sleep measurements and diary data
 - Serial collection of passive drool saliva samples for evaluation of cortisol concentrations
 - Objective measurements of sleep timing and quality through a wearable, accelerometry device (actigraphy)
 - Morning and evening daily diary completion to collect data related to sleep quality, health behaviours and stressors
- ACTH challenge (CST)
- *Ex vivo* cell culture analysis to evaluate cellular immunity through assessment of leukocyte inflammatory responses to a microbial challenge
- Semi-structured interview to assess perceptions of, and experiences related to, COVID-19

- A home visit to further understand the lived experience of long-COVID.

Further details can be found in the Psychiatric and Neuroendocrine Sub-Study Plan.

7.2.2.4 Sleep evaluation

Participants who are selected and provide consent for participation in the sleep sub-study, will have the following additional assessments:

- Repeated administration of questionnaires related to sleep and psychosocial factors
- Objective measurements of sleep performed within 60 days after the baseline visit:
 - Actigraphy with sleep diary for a week-long period
 - Overnight polysomnography (PSG) at the Wits Faculty of Health Sciences Sleep Laboratory at the end of the week-long actigraphy period.

Further details can be found in the Sleep Sub-Study Plan.

7.2.2.5 Pain evaluation

Participants who are selected and provide consent for participation in the pain sub-study, will attend a single visit where the following will be performed:

- QST (using the protocol developed by the German Network for Neuropathic Pain [40,41])
- CMT (using the protocol published by Lie et. al., 2017 [42])

Further details can be found in the Pain Sub-Study Plan.

7.2.2.6 Glucose metabolism evaluation

Participants who are not known diabetics, are not on treatment for diabetes mellitus (Type 1 or 2), and who have no history of diabetes or receiving treatment for diabetes mellitus (Type 1 or 2) prior to COVID-19 or asymptomatic SARS-CoV-2 infection, will be randomly selected for participation in the glucose metabolism sub-study. Those who provide consent for participation will attend a single visit where an OGTT, including measures of glucose, insulin, and c-peptide to estimate insulin sensitivity and beta-cell function, will be performed [16].

Further details can be found in Glucose Metabolism Sub-Study Plan.

